Title: Residual Gastric Volume Measured by Ultrasound in Diabetic Surgical Population Versus Non-diabetic Surgical Population.

NCT05435157

23/03/2022

**BACKGROUND:** Traditionally, diabetics have been considered patients with a high risk of aspiration due to having delayed gastric emptying; However, the evidence concerning residual gastric volume (GV) in fasting diabetic patients is inconsistent. This study aimed to compare the fasting GV of diabetic patients with or without dysautonomia with control patients scheduled for elective surgery using gastric ultrasound.

**METHODS:** Prospective, observational, single-blinded study. All adult patients, both those with DM and those without, who were scheduled for elective surgery under general or regional anesthesia, underwent assessment for eligibility to participate in the study. Written informed consent was obtained from all participants before enrollment. The inclusion criteria were as follows: body mass index (BMI)  $<40 \text{ kg.m}^{-2}$ ; age  $\geq 18$  years; ASA physical status I to III; individuals undergoing elective surgery who had the ability to understand the study rationale and provide informed consent. Exclusion criteria included pregnancy, recent upper gastrointestinal bleeding ( $<1$  month), abnormal anatomy of the upper gastrointestinal tract (such as hiatal hernias and gastric tumors), prior surgical procedures on the esophagus, stomach, or upper abdomen, gastroesophageal reflux disease, nondiabetic autonomic-neurological diseases, chronic kidney diseases, and previous use of prokinetics or opioids. Participants satisfying the inclusion criteria were consecutively enrolled as permitted by surgical programming and availability of research team members and were distributed in 2 groups (DM patients and controls) in a 1:1 ratio. According to the standard institutional practice, all patients underwent an 8-hour fasting period without solids and a 2-hour period without clear liquids before their scheduled elective surgery. Patients were permitted to take their regular morning medications with a sip of water 1 hour before the surgery. DM patients underwent an evaluation for the duration of DM, medication history, glycemic control assessed by glycosylated hemoglobin (HbA1c) levels, and symptoms of gastropathy (such as bloating/ abdominal distension, early satiety/postprandial fullness, nausea/vomiting, or abdominal pain/ discomfort). Additionally, other DM-related complications including diabetic nephropathy, diabetic retinopathy, diabetic vascular disease, and the presence of cardiovascular autonomic neuropathy (CAN; as an indicator of gastric dysautonomia) were documented for analysis. Patient demographics, ASA physical status, and treatments were also collected. During preoperative evaluation, assessment of

dysautonomia was conducted using 2 tests from the battery of standardized tests described by Ewing et al. al. The first test, performed with the patient at rest and in a supine position (requires having abstained from coffee or not having experienced a hypoglycemic episode the night before), involved monitoring heart rate variability by electrocardiography (ECG) while the patient breathed in and out at 6 breaths per minute. A difference in heart rate of  $>15$  beats per minute (bpm) was considered normal, while a difference of  $<10$  bpm

was considered abnormal. For the second test, the patient exhaled forcibly into a manometer mouthpiece to reach 40 mm Hg for 15 seconds while ECG monitoring was conducted. This maneuver was repeated 3 times with 1-minute intervals between each repetition. The Valsalva ratio, defined as the ratio of the longest R-R interval after the maneuver to the

shortest R-R interval during the maneuver, was calculated. The mean of the 3 Valsalva ratios was taken as the final value. Values of less than 1.10 were considered abnormal. In our study, a patient was classified as having dysautonomia if either of the 2 tests yielded positive results. Patients were categorized into 3 groups based on their DM history and the presence of dysautonomia: non-DM patients, DM patients with dysautonomia (DM-DYS), and DM patients without dysautonomia (DM-NDYS).

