### STATISTICAL ANALYSIS

The primary end point was the percentage of patients in each group with a Perlas grade 2 antrum. Based on an estimated prevalence of full stomach in fasting patients scheduled for elective surgery of approximately 5%, and a prevalence of gastroparesis in DM patients of around 15%, 141 patients per group would be required, assuming an alpha risk of 0.05 with a power of 80%. To account for an anticipated attrition rate exceeding 5%, we aimed to include a total of 296 patients (148 per group). Continuous data were presented as mean plus standard deviation (SD) for normally distributed data, and median plus interquartile

range (IQR) for nonnormally distributed data, after assessment of normality using the Shapiro-Wilk or Kolmogorov-Smirnoff test. Categorical variables were summarized as counts and percentages and were compared with a  $\chi^2$  test or Fisher exact test when appropriate. Group comparisons between patients with or without gastroparesis were performed using Student *t* test or the Mann-Whitney test as appropriate. Subgroup analyses were performed using 1-way analysis of variance (ANOVA), with post hoc Tukey-Kramer's method for pairwise subgroup comparison in the event of a positive ANOVA result. Alternatively, the Kruskal-Wallis test was used when ANOVA assumptions were not met, with the Dunn test for subgroup comparison in cases of a positive Kruskal- Wallis test result.

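### Glucose-lowering drugs that may slow gastric emptying are neither excluded nor analysed, so a drug effect could be attributed to diabetes

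*Combined protocol and SAP*

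**What the plan says.** The exclusion list in METHODS ends with "nondiabetic autonomic-neurological diseases, chronic kidney diseases, and previous use of prokinetics or opioids". No glucose-lowering class is named, restricted or excluded. The same section states: "Patients were permitted to take their regular morning medications with a sip of water 1 hour before the surgery".

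Drug data are collected. For the diabetic group, "DM patients underwent an evaluation for the duration of DM, medication history, glycemic control assessed by glycosylated hemoglobin (HbA1c) levels". More generally, "Patient demographics, ASA physical status, and treatments were also collected", wording that is not limited to diabetics.

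On grouping, "Patients were categorized into 3 groups based on their DM history and the presence of dysautonomia": non-diabetic, diabetic with dysautonomia (DM-DYS) and diabetic without (DM-NDYS). In STATISTICAL ANALYSIS, "The primary end point was the percentage of patients in each group with a Perlas grade 2 antrum". Categorical data are compared by chi-square or Fisher tests, and continuous data by t, Mann-Whitney, ANOVA or Kruskal-Wallis tests. There is no covariate model, no stratification by drug and no sensitivity analysis.

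**The concern.** By excluding prokinetic and opioid users, the plan treats drug effects on gastric emptying as something to keep out of the comparison. Drugs prescribed for diabetes itself are not handled in the same way. If some of them slow emptying, exposure follows the factor under study, because it is concentrated in the diabetic group by indication. Blinding the ultrasound operator to group does not remove this, since the drug would change the stomach and not the reading of it.

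The BACKGROUND section sets the study against the belief that diabetics empty slowly, and the diabetic group is split by a proposed mechanism. Readers will want to interpret a difference as an effect of diabetes or of autonomic neuropathy. An unadjusted comparison cannot separate that from a drug effect, and the variable that could help has no planned use.

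**Working it through.** **Inputs from the documents.** Control rate 5%, diabetic rate 15%, alpha 0.05, power 80%, 141 per group raised to 148 (STATISTICAL ANALYSIS); 1:1 ratio (METHODS).

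**Inputs assumed.** The documents give neither the share *f* of diabetics taking a drug that slows emptying nor the grade 2 rate *q* among users. I take *f* = 5-20% and *q* = 15-40%, with 5% grade 2 in everyone else and no use among controls. That any glucose-lowering drug slows emptying is itself general pharmacology and is not stated in the documents.

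**Step 1: the plan's own figure.** Pooled-variance formula, two-sided, with p̄ = 0.10:

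n = [1.960·√(2·0.10·0.90) + 0.842·√(0.05·0.95 + 0.15·0.85)]² / 0.10² = 140.1, rounded up to 141.

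This matches the plan. Power is 80.3% at 141 and 82.1% at 148. The sample size is not in dispute.

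**Step 2: diabetic rate with no disease effect.** Rate = (1 − f)·5% + f·q.

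**Step 3: chance of p<0.05 against 5% at 148 per group.** With p̄ the mean of the two rates, s₀ = √(2p̄(1 − p̄)/148), s₁ = √([p₁(1 − p₁) + p₂(1 − p₂)]/148) and d = p₂ − p₁, the upper-tail probability is 1 − Φ((1.960·s₀ − d)/s₁). The lower tail, Φ((−1.960·s₀ − d)/s₁), is added. For a diabetic rate of 12%: s₀ = 0.0324, s₁ = 0.0322, d = 0.07, so (0.0635 − 0.07)/0.0322 = −0.20 and the probability is 0.58.

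| f | q | Diabetic rate | Spurious difference | P(p<0.05), normal | P(p<0.05), exact enumeration of chi-square |
|---|---|---|---|---|---|
| 5% | 15% | 5.5% | 0.5 points | 0.05 | 0.05 |
| 10% | 20% | 6.5% | 1.5 points | 0.09 | 0.08 |
| 20% | 20% | 8.0% | 3.0 points | 0.18 | 0.17 |
| 20% | 40% | 12.0% | 7.0 points | 0.58 | 0.58 |

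The first row is the nominal error rate, that is, no material bias. The last is 7 of the planned 10 points.

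**Step 4: the dysautonomia contrast.** With the same *q* in both diabetic subgroups, the drug-induced difference between DM-DYS and DM-NDYS is (f_DYS − f_NDYS)·(q − 5%). It is zero when use is equal. At q = 40%, each 10-point gap in use moves the contrast by 0.10 × 0.35 = 3.5 points, in whichever direction the gap runs.

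**Step 5: cost of leaving users out.** Starting from 141 per group, with users removed from the diabetic group only and the remaining diabetics at the planned 15%:

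| f | Diabetics left | Power |
|---|---|---|
| 0% | 141 | 80.3% |
| 5% | 134 | 79.4% |
| 10% | 127 | 78.5% |
| 20% | 113 | 76.4% |
| 30% | 99 | 74.0% |

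**The case against.** The strongest reply is that the study can be read as descriptive. OUTCOMES asks for the prevalence of full stomach in diabetics and controls, and the study is observational with regular medication permitted. For diabetics as treated, a drug effect is part of the prevalence, and removing users answers a different question. This stands as a reason to leave the primary analysis alone. It does not cover a conclusion about diabetes or dysautonomia as the cause, which the BACKGROUND and the three-group split invite.

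Second, the mechanism and both numerical inputs come from outside the documents, and the 58% takes the top of both ranges. That is correct, and it is why the range has to start at no effect.

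Third, a reader might infer that the drug effect is confined to the diabetic group and will be mistaken for diabetes or dysautonomia. The documents do not support that. No rule bars controls (BMI up to just under 40) from such drugs, nothing shows that any participant took one, and the dysautonomia contrast is affected only if use is unequal between the two subgroups.

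Fourth, because medication history and treatments are recorded, a breakdown could be added later. That lowers the cost of repair, but an analysis chosen after the results are known carries less weight than a prespecified one.

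**Conclusion.** The concern holds in a conditional form. The plan excludes two groups of motility-altering drugs, leaves glucose-lowering drugs unrestricted, records medication and then does not use it. As written, it cannot separate a drug effect on gastric emptying from an effect of diabetes.

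The size is unknown. Under the assumed ranges, with no disease effect, the consequence runs from the nominal 5% chance of a significant result to about 58%. The documents do not say where in that range the study lies, so the upper figure should not set the severity. It would also be too strong to conclude that every statement must rest on non-users: that would replace the primary analysis, which is a legitimate estimate for diabetics as treated. What is missing is an inexpensive prespecified check before a difference is attributed to the disease. I rate it as something the plan should address, with medium confidence.

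**What to change.** Keep the primary analysis as planned, described as applying to diabetics as treated. Then add the following to STATISTICAL ANALYSIS:

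- From the medication history and treatments already collected, derive a flag for current use of a glucose-lowering drug that may slow gastric emptying, with the list of classes fixed in advance and applied to all groups, controls included. This depends on drug class having been recorded, which the plan does not state.
- Prespecify a sensitivity analysis repeating the DM versus control and DM-DYS versus DM-NDYS comparisons of Perlas grade 2 without flagged patients.
- Report the number of users in each of the three groups, and grade 2 prevalence in users and non-users.
- State that a difference will be attributed to diabetes or dysautonomia itself only if it is consistent in the sensitivity analysis.

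The cost is one derived variable and one repeated analysis, with no new enrolment and no change to any patient's treatment. The sensitivity analysis has fewer diabetics and somewhat less power, as shown in Step 5. It may also introduce selection if drug use tracks disease duration, HbA1c or BMI, so those characteristics should be tabulated for users and non-users alongside it.

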### Ultrasound Assessments

On the day of surgery, gastric ultrasound scans were performed in the preoperative room before anesthesia induction by a skilled operator, who was blinded to the patient's study group. A GE LOGIQ e R7 series ultrasound machine with abdominal presets was used to acquire a cross-sectional view of the antrum in the sagittal plane at the level of the liver and aorta using a C1-5 curvilinear probe (3–5 MHz) positioned in the epigastrium. Scans were performed in 2 positions: supine with the upper body elevated at 45° and RLD, after the protocol outlined by Perlas et al. Qualitative data regarding the nature of gastric content (empty, clear fluid, thick fluid/solid) were collected based on sonographic findings. Additionally, the sonographic appearance of the gastric antrum was categorized using the 3-point grading scale established by Perlas et al. Grade 0 denoted the absence of any content appearance (a flat antrum with juxtaposed anterior and posterior walls) in both the semi-upright and RLD positions. Grade 1 indicated the presence of fluid appearance solely in the RLD position, while Grade 2 signified the presence of any content appearance in both the RLD and supine positions. For volume assessment, the antral CSA was measured at the level of the aorta, with the antrum in a resting state (between peristaltic contractions), and 3 consecutive measurements were taken in the RLD position. These measurements were averaged to estimate GV, aiming to minimize measurement errors. During this process, the CSA was measured using the free-tracing tool of the equipment, encompassing the entire thickness of the gastric wall. The estimated GV was calculated using the mathematical model proposed by Perlas et al, based on the CSA of the gastric antrum in the RLD position. The calculation is as follows:  $\text{volume (mL)} = 27.0 + 14.6 \times \text{CSARLD (cm}^2) - 1.28 \times \text{age (years)}$ .

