### OUTCOMES

Our primary outcome was to assess the prevalence of full stomach using the Perlas gastric content grading scale in diabetic patients with or without dysautonomia, as well as in healthy controls. Secondary outcomes included measuring the CSA and GV in RLD, as well as determining the prevalence of solid gastric residue.

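### By the plan's own volume formula, antral CSA rises with age at equal gastric volume, but the CSA comparison has no age term

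*Combined protocol and SAP*

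**What the plan says.** The Ultrasound Assessments section averages three tracings of the antrum in the right lateral decubitus (RLD) position, each "encompassing the entire thickness of the gastric wall", and converts the mean to a volume "based on the CSA of the gastric antrum in the RLD position. The calculation is as follows": volume (mL) = 27.0 + 14.6 × CSA (cm²) − 1.28 × age (years).

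The Outcomes section makes both quantities outcomes: "Secondary outcomes included measuring the CSA and GV in RLD".

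Under Methods, adults of 18 or over are eligible, with no upper age limit stated. Patients are enrolled consecutively and "were distributed in 2 groups (DM patients and controls) in a 1:1 ratio". The study is observational, and no matching, stratification or other control for age is described.

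For continuous data, the Statistical Analysis section lists the t test or Mann-Whitney test for two groups. The three-group sentence opens "Subgroup analyses were performed using 1-way analysis of variance (ANOVA", then names Tukey-Kramer follow-up, with Kruskal-Wallis and Dunn as the alternative. No regression model, covariate or rule for negative calculated volumes appears.

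**The concern.** The plan adopts a model in which antral area depends on age as well as on content. It uses that model to obtain GV, then also treats CSA as an outcome in its own right with nothing to take age out. If the diabetic patients are older on average than the controls, their antra will, on the plan's own model, be larger at identical gastric volume.

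The result could be a significant CSA difference, readily taken as evidence of more retained gastric content in diabetics, beside a GV comparison that shows none. The same applies among the three subgroups (controls, diabetics with dysautonomia, diabetics without) if their mean ages differ. Rank tests give no protection, because the age effect is a shift in location.

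**Working it through.** **The plan's own figure.** The 141 per group belongs to the primary endpoint (5% versus 15%), but it is the group size used below. With two-sided alpha 0.05, power 80%, pooled variance and no continuity correction:

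n = [1.96 × √(2 × 0.10 × 0.90) + 0.842 × √(0.05 × 0.95 + 0.15 × 0.85)]² / 0.10² = 140.1, rounded up to 141.

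This agrees with the plan. Nothing in this point changes the sample size.

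**Age shift in CSA at equal volume.** Solve the formula for CSA:

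CSA = (GV − 27.0 + 1.28 × age) / 14.6

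- Per year of age: 1.28/14.6 = 0.0877 cm².
- A 5-year gap in mean age gives 0.44 cm²; a 10-year gap gives 0.88 cm².
- Example: a volume of 50 mL corresponds to (50 − 27 + 64)/14.6 = 5.96 cm² at age 50 and (50 − 27 + 89.6)/14.6 = 7.71 cm² at age 70.

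**Chance of a significant unadjusted CSA test when true volume is equal.** The assumptions are two groups of 141, a two-sided 5% test and a CSA SD of 2 to 4 cm². The SD and the age gap are not in the documents. With SE = SD × √(2/141) and d the shift above, the chance is P(|Z + d/SE| > 1.96).

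| CSA SD (cm²) | SE (cm²) | 5-year gap | 10-year gap |
|---|---|---|---|
| 2 | 0.238 | 45% | 96% |
| 2.5 | 0.298 | 31% | 84% |
| 3 | 0.357 | 23% | 69% |
| 4 | 0.476 | 15% | 45% |

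The nominal rate is 5%. At the full recruitment target of 148 per group the ranges are 16% to 47% and 47% to 97%. Subgroup sizes by dysautonomia are not given, so no figure is offered for the three-group test.

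**Negative volumes (minor).** GV is below zero when CSA < (1.28 × age − 27)/14.6:

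- Age 65: (83.2 − 27)/14.6 = 3.85 cm².
- Age 75: (96 − 27)/14.6 = 4.73 cm².

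If CSA at age 65 were normal with mean 4 to 6 and SD 1.5 to 2.5 cm² (assumed), the share below 3.85 would run from 8% (mean 6, SD 1.5) to 48% (mean 4, SD 2.5). Small antra are to be expected: grade 0 is defined as "a flat antrum with juxtaposed anterior and posterior walls", and the sample-size assumption is that only about 5% of fasting elective patients have a full stomach.

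**The case against.** The strongest reply is that GV is reported beside CSA and already contains the age term. A group difference in GV divided by 14.6 is a CSA difference corrected with the formula's own coefficient, so the age shift is removed in the companion outcome. That stands for GV. It does not help a reader who interprets the CSA result by itself, and the plan lists CSA as a separate outcome.

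A second reply is that the Statistical Analysis section never pairs CSA or GV with a named test, and its two-group sentence speaks of patients with or without gastroparesis. That the CSA comparison is unadjusted is an inference. It is a fair one, because no other method for continuous data is listed.

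A reader might also infer more than the documents support:

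- *That the groups differ in age.* No ages are given. The documents show only that nothing in the design makes ages equal.
- *That GV, too, is compared without regard to age.* It is not, since age enters through the formula.
- *That the plan will average impossible negative volumes.* Means are reserved for normally distributed data; otherwise medians and rank tests already apply. What is missing is a statement of how negative values are treated.
- *That negative volumes pile up in the older group alongside the CSA bias.* The two belong to different scenarios. At equal volume, calculated GV has the same distribution at every age: with SD 2, age 55 and mean CSA 5 cm² give 15.5% negative, as do age 65 and mean 5.877 cm². An excess in older patients needs equal CSA instead (28% at age 65, mean 5 cm²), where calculated volumes are no longer equal.
- *That negative values should be set to zero.* This itself alters group differences. At equal CSA (mean 5, SD 2 cm²), it shrinks the difference in mean GV between ages 55 and 65 from 12.8 mL to about 10.0 mL.

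**Conclusion.** The point holds for the secondary CSA outcome. The slope of 0.088 cm² per year follows directly from the printed formula, and neither the design nor the listed tests control for age. How much this matters in practice depends on an age gap and a CSA SD that the documents do not give. Over the assumed ranges, the chance of a false-positive CSA result is three to nine times the nominal 5% for a 5-year gap (15% to 45%), and nine to nineteen times for a 10-year gap (45% to 96%). With no age gap there is no excess.

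The primary endpoint (Perlas grade 2) and the sample size do not use the formula, and the GV comparison already includes age; none of these is called into question here. The absence of a rule for negative GV is a reporting gap and no more than that.

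**What to change.** In the Statistical Analysis section, state that CSA will be compared between diabetics and controls, and among the three subgroups, with a linear model containing group and age. State also that the unadjusted CSA difference will not be interpreted as a difference in gastric content.

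For GV, state that the number of negative calculated values will be reported per group, and that the values will be kept as calculated in a rank-based comparison.

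The cost is a few sentences of SAP text. Age is already needed to compute GV, so no new data are required and the sample size does not change.

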### OUTCOMES

Our primary outcome was to assess the prevalence of full stomach using the Perlas gastric content grading scale in diabetic patients with or without dysautonomia, as well as in healthy controls. Secondary outcomes included measuring the CSA and GV in RLD, as well as determining the prevalence of solid gastric residue.

